16.2. Secondary Efficacy

The secondary efficacy analyses will be performed for the mITT.

16.2.1. Secondary Efficacy Variables & Derivations

The TOSS is a composite score calculated as the sum of red/burning eyes, tearing, itchy/watery eyes scores (maximum 9). The individual scores are collected in e-diary. The AUC will be computed using the linear trapezoidal method (22) for all the variables below. The mean score and its 95% CI will be plotted across respective timepoints. This plot will also include the LS mean and 95% CI of the AUC.

- AUC of TOSS from H0 to H6 at V4
- AUC of TNSS-3 from H0 to H12 at V4
- AUC of TOSS from H0 to H12 at V4
- AUC of TNSS-3 from randomization (D1) to V4 (D4)
- AUC of TOSS from randomization (D1) to V4 (D4)

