Randomization may occur within a week after completion of the washout period, where the participants will be instructed not to take the study drug until 2 days before their planned V4. The participants will consume study drug at home, on Day 2 and Day 3. This will be followed by a Ragweed pollen challenge lasting 3 hours (standard Ragweed pollen concentration of 3500 ± 500 grains/m³) at V4 (Day 4). During this challenge, participants in both Arms will receive a single dose of fexofenadine 180 mg after pollen exposure, at Hour 3. The participants will be discharged after the challenge at V4 (Day 4). Participants will record their symptoms using a diary card (or an e-diary, if applicable) while in the EEU and at home thereafter. On Day 5, all participants will participate in a telephonic visit, which will be recorded as End-of-Study (EOS) Visit. For return of the e-diary, the participants will come to the study site for an in-person EOS Visit.

Number of Participants:

An adequate number of participants will be screened to achieve 96 participants randomized (86 evaluable participants).

Adult patients (18 to 80 years old) suffering from seasonal allergic rhinitis (SAR) provoked by Ragweed pollen, with a 2-year history of SAR with positive skin prick test to Ragweed allergen at screening (≥ 3 mm) and having a TNSS-3 of ≥ 4 (with 3 nasal symptoms) at first pollen challenge at Visit 2 will be enrolled. Any participant with history of anaphylaxis to Ragweed pollen, history of asthma or exacerbations in the past 12 months requiring regular inhaled corticosteroids for >4 weeks per year, any oral corticosteroid usage, any emergency department visit for asthma or any asthma-related hospitalization, or history of chronic sinusitis will be excluded.

Intervention Groups and Duration:

[figure not shown]
Participants in Arm A (active 2 days) will consume at home, 1 tablet of fexofenadine 180 mg each day in the morning on Day 2 and Day 3, followed by 1 tablet of fexofenadine 180 mg after the pollen challenge on Day 4.

Participants in Arm B (placebo 2 days) will consume at home, 1 tablet of matching placebo each day in the morning on Day 2 and Day 3, followed by 1 tablet of fexofenadine 180 mg after the pollen challenge on Day 4.

Data Monitoring/Other Committee: No

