4.0 STUDY DESIGN

4.1 Overall Design

This is a Phase IIIb, randomized, double-blind, single-center, two-arm, parallel-group, placebo-controlled, proof-of-concept study, outside of Ragweed pollen season. Two Arms are planned:

- Arm A (active 2 days): two days of pre-treatment with fexofenadine, then fexofenadine 180 mg during the test pollen challenge
- Arm B (placebo 2 days): two days of pre-treatment with placebo, then fexofenadine 180 mg during the test pollen challenge

A total of 5 visits to the study site or the EEU are planned per participant.

An adequate number of participants will be screened to achieve 96 participants randomized (86 evaluable participants). Each participant will be screened, including skin prick tests at Visit 1 (V1). Eligible participants will return to the study site for a 3-hour pollen exposure (standard Ragweed pollen concentration of 3500 ± 500 grains/m³) at V2 and discharged thereafter. Only those participants with qualifying symptom scores (Total Nasal Symptom Score of 3 symptoms [TNSS-3] ≥ 4) in the last 90 minutes of the challenge will be eligible to be randomized into the study. After a washout period of at least 15 days, randomization will occur within a week, at V3 (Day 1) in a 1:1 proportion to either Arm A (active-active) or Arm B (placebo-active) group. Randomization may occur within a week after completion of the washout period, where the participants will be instructed not to take the study drug until 2 days before their planned V4. The participants will consume study drug at home, on Day 2 and Day 3. This will be followed by a Ragweed pollen challenge lasting 3 hours (standard Ragweed pollen concentration of 3500 ± 500 grains/m³) at V4 (Day 4). During this challenge, participants in both Arms will receive a single dose of fexofenadine 180 mg after pollen exposure, at Hour 3 (H3). The participants will be discharged after the challenge at V4 (Day 4). Participants will record their symptoms using a diary card (e-diary) while in the EEU and at home thereafter. On Day 5, all participants will participate in a telephonic visit, which will be recorded as End-of-Study (EOS) Visit. For return of the e-diary, the participants will come to the study site for an in-person EOS Visit. Any emergency/pandemic concerns in the future will be minimized via use of an e-diary, which is a virtual interface, to document AEs, concomitant medications, symptoms, and the treatment satisfaction questionnaire.

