4.1.3 Washout Period (≥ 15 Days)

The following information will be recorded every day preferably in the morning, via e-diary:

- Any AEs
- Concomitant medications

During the washout period of at least 15 days, any antiallergic therapy is forbidden. Please see [Section 6.8](#) for prohibited medications during the study, including the washout period.

4.1.4 Visit 3 (Randomization) Day 1

Randomization may occur within a week after completion of washout period. The following procedures will be performed on Day 1:

- Inclusion/exclusion criteria verification
- Urine pregnancy testing (for WOCBP only)
- E-diary completion
- Concomitant medication recording
- Collection of AEs
- Baseline allergic symptoms scoring
- Randomization will be performed as follows:
 - Arm A: Fexofenadine, one tablet of 180 mg in the morning for 2 days
 - Arm B: Placebo, one tablet in the morning for 2 days

4.1.5 At Home: Day 2 and Day 3 (Study Drug Intake and Diary Card Completion)

The following activities are to be completed at home in the morning on Day 2 and Day 3:

- Diary card (e-diary) completion for:
 - Allergic symptom scores, before drug intake: instantaneous assessments
 - Any AEs
 - Concomitant medications
- Study drug intake

4.1.6 Visit 4 (Test Ragweed Pollen Challenge) Day 4

The following activities are to be completed in the morning:

- Inclusion/exclusion criteria verification
- Urine pregnancy testing (for WOCBP only) before challenge
- COVID-19 testing via a rapid antigen test for SARS-CoV-2 infection before challenge
- Return study drug wallet before challenge
- Symptoms scoring before challenge
- Starting pollen challenge (hour zero [H0]): all participants will be exposed to a standard Ragweed pollen concentration of 3500 ± 500 grains/m³

If in the judgment of the Investigator, symptoms become intolerable the participants will be removed from the EEU.

- Pollen exposure will last 3 hours (H0 to H3).
 - H0 to H3: symptoms evaluation every 15 minutes
 - At H3: stop pollen exposure
 - At H3 all participants will receive one packet of fexofenadine 180 mg and will be instructed to take one tablet from the pack:
 - Arm A: single dose of fexofenadine 180 mg
 - Arm B: single dose of fexofenadine 180 mg
- H3 to H6: symptoms evaluation every 30 minutes

- At H6:
 - Physical examination
 - Vital signs
 - Nasal examination as per Investigator judgment
- Concomitant medication recording
- Participants will be questioned with regards to AEs

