7.5. Multiple Comparisons/ Multiplicity

The following multiplicity testing procedures will be used to control the type I error:

- The secondary efficacy endpoints will be tested only if the primary endpoint is significant.
- The multiplicity of secondary efficacy endpoints will be handled using Hochberg's step-up test.
- For the other secondary efficacy endpoints and the exploratory efficacy endpoints, p-values will be provided for descriptive purpose only.
- The number of Adverse Events defined as other secondary endpoint will be analysed only with descriptive statistics (no p-value will be provided).

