16.2.3. Analysis of Secondary Efficacy Variables

16.2.3.1. ANALYSIS OF SECONDARY VARIABLES BASED ON AUC

All secondary endpoints based on the AUC (i.e., TNSS-3 and TOSS) will be analysed using an ANCOVA model,

Document:	[REDACTED]	
Author:	Version Number:	[REDACTED]
	Version Date:	[17Feb2023]
Template No.:	Reference:	[REDACTED]
Effective Date:	[REDACTED]	
[REDACTED]		

with treatment group as fixed effect and the baseline values as covariate. For the AUC assessment starting from Randomization (D1) to D4, symptom scoring at D1 will be used as baseline.

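### The two D1-to-V4 AUC secondary endpoints adjust for the D1 score only, leaving the equally pre-dose D2 score in the outcome as avoidable noise; the end of the window on Day 4 is not defined

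*SAP*

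**What the plan says.** SAP 16.2.1 names five secondary efficacy AUCs. Three use challenge-day scores at V4 (TOSS to H6, TNSS-3 to H12, TOSS to H12). The other two run from randomization to V4: "AUC of TNSS-3 from randomization (D1) to V4 (D4") and its TOSS counterpart. On the calculation it says: "The AUC will be computed using the linear trapezoidal method (22) for all the variables below". It does not mention dividing by elapsed time, and it does not say whether the D1-to-V4 window stops at the pre-challenge score or takes in the challenge scores.

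For the covariate, SAP 16.2.3.1 says of the D1-to-D4 AUCs that "symptom scoring at D1 will be used as baseline".

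The timing of scores and doses comes from the Protocol. Section 4.1.4 schedules "Baseline allergic symptoms scoring" on Day 1. The Synopsis states: "The participants will consume study drug at home, on Day 2 and Day 3". For those two mornings, section 4.1.5 asks for "Allergic symptom scores, before drug intake: instantaneous assessments". Section 4.1.6 has one further score before the challenge on Day 4.

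On multiplicity, SAP 7.5 says: "The multiplicity of secondary efficacy endpoints will be handled using Hochberg's step-up test". The same section makes other secondary efficacy endpoints descriptive, without listing them.

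**The concern.** A score taken before the first tablet cannot respond to treatment. In these two endpoints that applies to D1 and also to D2, because the D2 score is recorded before that morning's dose. An AUC that includes them carries weight that adds variance and no treatment effect. ANCOVA can remove such variance when the pre-dose scores are covariates, but the plan uses only one of the two.

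What is at stake is the power and precision of two secondary endpoints. If both sit in the Hochberg family and fail to reach significance, they also tighten the thresholds for the three V4 AUCs.

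**Working it through.** **The plan's own figure.** Protocol 9.5 gives design figures for the primary endpoint only: difference 10.5, SD 15, 90% power, two-sided 5%. Per arm, n = 2 × (1.960 + 1.282)² × 15² / 10.5² ≈ 42.9, so 43, or 86 in total; 86 / 0.90 = 95.6, so 96 randomized. Both figures reproduce. The documents give no weights, SD or power for the D1-to-V4 AUCs, so the steps below rest on stated assumptions.

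**Step 1: trapezoid weights.** Each score's weight is half the gap on either side of it. With daily scores and a window ending at the pre-challenge/H0 score, D1, D2, D3 and D4 weigh 12, 24, 24 and 12 hours.

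| Window ends | Total (h) | D1 + D2 (h) | Pre-dose share | D2 alone |
|---|---|---|---|---|
| Pre-challenge/H0 | 72 | 36 | 50% | 33% |
| H6 | 78 | 36 | 46% | 31% |
| H12 | 84 | 36 | 43% | 29% |

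**Step 2: what D1 adjustment removes.** Take the window ending before the challenge, in days: AUC = 0.5·D1 + D2 + D3 + 0.5·D4. With D1 in the model, subtracting 0.5·D1 from the outcome leaves the treatment estimate and residual variance unchanged, so D1's weight costs nothing. D2's weight of 1 in 3 remains.

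**Step 3: gain from adding D2.** Assume SD 1 on each day, effect δ on D3 and D4, none on D1 and D2, and day-to-day correlation ρ. The effect on the AUC is 1.5δ under either model, so only the residual variance changes.

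Worked case, compound symmetry, ρ = 0.4:
- Var(AUC) = 2.5 + 0.4 × (9 − 2.5) = 5.1.
- Cov(AUC, D1) = 0.5 + 0.4 × 2.5 = 1.5.
- D1 only: residual variance 5.1 − 1.5² = 2.85.
- D1 and D2: given both, D3 and D4 each have variance 1 − 2(0.16)/1.4 = 0.771 and covariance 0.4 − 0.229 = 0.171. Residual variance is 1.25 × 0.771 + 0.171 = 1.136.
- Variance ratio 2.85 / 1.136 = 2.5; effect-size ratio √2.5 ≈ 1.58.

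| Correlation | D1 only | D1 + D2 | Variance ratio | Effect-size ratio |
|---|---|---|---|---|
| Compound symmetric, 0.4 | 2.85 | 1.14 | 2.5 | 1.58 |
| Compound symmetric, 0.8 | 1.45 | 0.45 | 3.2 | 1.80 |
| AR(1), 0.4 | 3.26 | 1.42 | 2.3 | 1.52 |
| AR(1), 0.8 | 2.41 | 0.80 | 3.0 | 1.74 |

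By the argument of step 2, once D2 is a covariate its weight in the outcome is irrelevant. Starting the AUC at D2 gives exactly the same figures.

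**Step 4: elapsed time.** On a fixed three-day grid, dividing by time divides every AUC by the same constant and changes no p-value. It matters only if the D1–D4 length varies. A D1-to-D2 gap of 16 h gives a length of 2.67 days, 28 h gives 3.17 days, and 48 h (dosing one day later) gives 4.0 days.

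**Step 5: Hochberg.** The strictest threshold is 0.05/5 = 0.01 in a family of five and 0.05/3 = 0.0167 in a family of three. Simulation with 400,000 draws assumed no effect on the two D1-to-V4 AUCs, correlations of 0.6–0.85 among the three V4 AUCs, and 0.5 between the two null endpoints.

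| Assumption for each V4 secondary | Average power, family of five | Family of three |
|---|---|---|
| 80% unadjusted power | 63% | 75% |
| Effect size 0.70, 43 per arm | 78–79% | 87% |

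**The case against.** The strongest reply is that the planned test is better than the raw weights suggest. D1 is already adjusted for, so it is wrong to say that half the weight dilutes the test. That stands: the remaining problem is D2.

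A second reply is that the study is off-season with no challenge until V4, so there may be little effect to find, and multiplying a null effect leaves it null. That also stands for power. The narrower interval would still be gained.

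A third is that D2 is scored after randomization. It is nonetheless scored before the first tablet under blinded assignment, so treatment should not influence it, provided the diary entry does precede intake.

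Several stronger readings are tempting, and the documents do not support them:

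- **The AUC could triple because the interval might run from 3 to 9 days.** Protocol 4.1 says "participants will be instructed not to take the study drug until 2 days before their planned V4", which could suggest a long wait. But Protocol 5.5 caps involvement after randomization at 5 days, the schedule fixes D1 to D4, and the one-week allowance runs from the end of washout to randomization. The wording on waiting calls for reconciliation with the cap and does not establish a tripling.
- **The endpoints must be redefined to start at D2.** Step 3 shows that this adds nothing once D2 is a covariate.
- **They occupy two of five Hochberg places and must be removed.** Five is the natural reading, but the unnamed other secondary efficacy endpoints leave it open. The secondary objective includes prevention of symptoms, so keeping these endpoints in the family is a trade-off for the sponsor. The step 5 figures also ignore the gate on the primary. Given a significant primary, the effect-size-0.70 case is about 83–86% versus 92–94%.

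**Conclusion.** The point holds as an avoidable loss of precision. D1 and D2 are both pre-dose and only D1 is adjusted for. D2, with one third of the weight for a window ending before the challenge, stays in the outcome although it is already collected and could be a covariate.

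Adding it would raise the standardised effect about 1.5–1.8 fold. That rests on equal SDs, an equal effect on D3 and D4, correlation of 0.4–0.8 and a window ending before the challenge; the documents supply none of these, and the gain was not calculated for windows to H6 or H12. If off-season scores cluster near zero, the equal-SD assumption is rough and the range is only indicative.

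The undefined window end and the unnamed Hochberg family are gaps in their own right. A reader might infer bias or a threat to the main result. Neither follows: the pre-dose noise is the same in both randomized arms, and the primary endpoint uses V4 scores only.

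**What to change.** - **SAP 16.2.3.1:** for the two D1-to-V4 AUCs, use both the D1 and the D2 pre-dose scores as covariates.
- **SAP 16.2.1:** state which Day 4 score ends the window.
- **Protocol 4.1 and 5.5:** reconcile the wording on when dosing starts relative to V4 with the 5-day maximum. If the D1–D4 length can vary, specify the AUC divided by elapsed time; if it is fixed, no change is needed.
- **SAP 7.5:** name the members of the Hochberg family. Whether the two D1-to-V4 AUCs belong in it is for the sponsor to weigh against the figures in step 5.

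The cost is SAP wording before database lock, a note in SAP 3.3, and one extra covariate. No new data are needed. A participant with no D2 score would fall under the interpolation rule in SAP 7.3. That rule would draw on D3, a score taken after the first tablet, so the SAP should say how a missing D2 covariate is handled.

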16.2.2. Intercurrent Event Handling and Data Imputation for Secondary Efficacy Variable(s)

Not Applicable.

16.2.3. Analysis of Secondary Efficacy Variables

16.2.3.1. ANALYSIS OF SECONDARY VARIABLES BASED ON AUC

All secondary endpoints based on the AUC (i.e., TNSS-3 and TOSS) will be analysed using an ANCOVA model,

Document:	[REDACTED]	
Author:	Version Number:	[REDACTED]
	Version Date:	[17Feb2023]
Template No.:	Reference:	[REDACTED]
Effective Date:	[REDACTED]	
[REDACTED]		

with treatment group as fixed effect and the baseline values as covariate. For the AUC assessment starting from Randomization (D1) to D4, symptom scoring at D1 will be used as baseline.

16.2.3.2. ANALYSIS OF TNSS-3, TOSS, AND TSS

The TNSS-3, TOSS, TSS, and individual symptom score by time point will be analysed given the mean and 95% confidence interval (CI).

The TNSS-3, TOSS, and TSS will be analysed using MMRM (Mixed Models for Repeated Measures), with treatment, time point and treatment group by time point interaction as fixed effect with their respective H0 scores as baseline covariate. The MMRM model will be run using PROC MIXED procedure with an unstructured correlation matrix to model the within-subject errors. If unstructured fails to converge, the following covariance structures will be tested: CS (compound symmetric) first, and then AR (1) (first-order autoregressive). Denominator degrees of freedom will be estimated using the Satterthwaite's approximation.

The descriptive statistics (number, mean, SD, median, Q1 and Q3, minimum, and maximum) of AUC and the statistics from the MMRM, least square (LS) means, standard errors (SEs) and 95% confidence intervals (CIs)) will be provided.

16.3. Exploratory Efficacy

[REDACTED]

Document: [REDACTED]

Author: [REDACTED]

Version Number: [REDACTED]

Template No.: [REDACTED]

Version Date: [17Feb2023]

Effective Date: [REDACTED]

Reference: [REDACTED]

[REDACTED]

16.3.2. Intercurrent Event Handling and Data Imputation for Exploratory Efficacy Variable(s)

Not applicable.

16.3.3. Analysis of Exploratory Efficacy Variables

A series of five horizontal black bars of varying lengths, decreasing from left to right. The first bar is the longest, followed by a shorter one, then a medium one, then another short one, and finally the shortest bar on the far right.

17. QUALITY OF LIFE ANALYSIS

Not applicable.

18. SAFETY OUTCOMES

All outputs for safety outcomes will be based on the SAE.

Document: [REDACTED]
Author: [REDACTED] Version Number: [REDACTED]
Template No.: [REDACTED] Version Date: [17Feb2023]
Effective Date: [REDACTED]
[REDACTED]

There will be no statistical comparisons between the treatment groups for safety data, unless otherwise specified with the relevant section.

18.1. Adverse Events

Adverse Events (AEs) will be coded using Medical Dictionary for Regulatory Activities (MedDRA) Version 25.1.

The pre-treatment period starts the day of the signed informed consent and ends before administration of study drug. The treatment-emergent AE period starts at time of administration of study drug ends 3 days after administration of study drug.

See Appendix 2 for handling of partial dates for AEs. In the case where it is not possible to define an AE as treatment emergent or not, the AE will be classified by the worst case, i.e., treatment emergent.

An overall summary of number of subjects within each of the categories described in the sub-section below, will be provided as specified in the templates.

Listings will include pre-treatment AEs and TEAEs.

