6.1 Study Drug(s) Administered

Table 2 Study Drugs Administered

Study Drug Label	Active drug	Placebo
Study Drug Name	marketed 180 mg fexofenadine HCl	placebo
Study Drug Description	peach, oblong, film-coated oral tablet, with “018” on one side, scripted “e” on the other side.	indistinguishable from active drug
Type	drug	drug
Dose Formulation	tablet	tablet
Unit Dose Strength(s)	180 mg fexofenadine HCl per tablet	0 mg fexofenadine HCl per tablet
Dosage Level(s)	1 tablet once daily	1 tablet once daily
Route of Administration	oral	oral
Use	active drug	placebo
IMP and NIMP/AMP	IMP	IMP
Sourcing	Provided centrally by Sanofi Consumer Health Care	Provided centrally by Sanofi Consumer Health Care
Packaging and Labeling	Randomized, double-blind, placebo-control study part: Fexofenadine HCl 180 mg and matching placebo will be provided as identical film-coated tablets and packaged in child-resistant wallets (containing a blister of 3 tablets of fexofenadine 180 mg or matching placebo – 2 doses and 1 additional tablet in case of loss). Post pollen challenge, open-label study part: Fexofenadine HCl 180 mg will be provided as film-coated tablets and packaged in US commercial Allegra® 5-ct blister packs with open labeling (one pack per participant). The content of the labeling will be in accordance with local regulatory specifications and requirements.	
Current Name	Allegra® (fexofenadine)	Matching placebo

Abbreviations: AMP = auxiliary medicinal product, IMP = investigational medicinal product,

NIMP = non-investigational medicinal product.

Table 3 Study Arms

Arm Title	Arm A	Arm B
Arm Type	Active 2 days	Placebo 2 days
Arm Description	
During the randomized, double-blind, placebo-control study part, participants will take 1 tablet of fexofenadine 180 mg each day in the morning on Day 2 and Day 3.
 
During the open-label study part, participants will take 1 tablet of fexofenadine 180 mg after the pollen challenge on Day 4
	
During the randomized, double-blind, placebo-control study part, participants will take 1 tablet of matching placebo each day in the morning on Day 2 and Day 3.
 
During the open-label study part, participants will take 1 tablet of fexofenadine 180 mg after the pollen challenge on Day 4

Associated Study Drug Labels	Active drug	Placebo

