8.3 Adverse Events, Serious Adverse Events, and Other Safety Reporting

The definitions of AEs and SAEs can be found in [Section 10.2](#).

Adverse events will be reported by the participant (or, when appropriate, by a caregiver, surrogate, or the participant's legally authorized representative).

The Investigator and any qualified designees are responsible for detecting, documenting, and recording events that meet the definition of an AE or SAE and remain responsible for following up all SAEs, AEs related to study drug, or AEs that lead to discontinuation from the drug or study (see [Section 7.0](#)).

The method of recording, evaluating, and assessing causality of AEs and SAEs and the procedures for completing and transmitting SAE reports are provided in [Section 10.2](#).

8.3.1 Time Period and Frequency for Collecting Adverse Event and Serious Adverse Event Information

All AEs and SAEs will be collected from the signing of the informed consent form (ICF) until EOS, at the time points specified in the SoA ([Section 1.3](#)).

Medical occurrences that begin before the start of study drug but after obtaining informed consent will be recorded as medical history/current medical conditions, not as AEs.

All SAEs will be recorded and reported to the Sponsor or designee immediately and under no circumstance should this exceed 24 hours of the Investigator's awareness of the event, as indicated in [Section 10.2](#) and [Section 10.3](#). The Investigator will submit any updated SAE data to the Sponsor or designee within 24 hours of their awareness of the updated information.

Investigators are not obligated to actively seek information on AEs or SAEs after conclusion of the study participation. However, if the Investigator learns of any SAE, including a death, at any time after a participant has been discharged from the study, and he/she considers the event/cause of death to be reasonably related to the study drug or study participation, the Investigator must promptly notify the Sponsor or designee.

The method of recording, evaluating, and assessing causality of AE and SAE and the procedures for completing and transmitting safety reports are provided in [Section 10.2](#) and [Section 10.3](#).

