5.5. Safety Analysis Set [SAF]

The safety analysis set (SAF) will contain all subjects in the ITT set who receive at least one dose of study medication and subjects will be classified according to treatment received.

If there is any doubt whether a subject was treated or not, they will be assumed treated for the purposes of analysis.

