7. STATISTICAL CONSIDERATIONS

Unless otherwise specified, all statistical tables will be provided by treatment group and will first present the results in the active group (FEXPRESAR) and then the results in the placebo group. The column ‘overall’ displaying all patients (all treatment groups combined) will be presented where appropriate.

The descriptive summary for continuous data will include the number of non-missing observations (n), mean, standard deviation, median, 25th percentile and 75th percentile, minimum, and maximum. The number of subjects with missing data will be displayed when relevant.

Categorical data will be summarized for each treatment group using counts (n) and percentages (%). The number of subjects with missing data will be displayed when relevant, but it will not be included in the denominator for the calculation of percentages unless otherwise specified.

If the original data has N decimal places, then the summary statistics will have the following decimal places:

- Minimum and maximum: N
- Mean, median, percentiles, confidence intervals, ratios: N + 1

Document:	[REDACTED]	
Author:	Version Number:	[REDACTED]
	Version Date:	[17Feb2023]
Template No.:	Reference:	[REDACTED]
Effective Date:		[REDACTED]
[REDACTED]		

- SD: N + 2

Percentages will be reported to one decimal place. P-values should be reported to three decimal places, except values <1.000 but >0.999 will be presented as ‘>0.999’ (e.g., 0.9998 is presented as >0.999); and values <0.001 will be presented as ‘<0.001’ (e.g., 0.0009 is presented as <0.001)

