18.1.1. All TEAEs

Incidence of TEAEs will be presented by System Organ Class (SOC) and Preferred Term (PT) and broken down further by maximum severity and relationship to study medication.

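### TEAE tables run over one undivided period, so the placebo column includes time after open-label fexofenadine, and the TEAE window names no anchor dose

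*SAP*

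**What the plan says.** **Dosing.** Protocol 4.1 sets the blinded doses: "The participants will consume study drug at home, on Day 2 and Day 3". Protocol 6.1 (Table 3) then states, for both arms, that in the open-label part "participants will take 1 tablet of fexofenadine 180 mg after the pollen challenge on Day 4"; section 4.1.6 places this dose at H3. Protocol 6.0 counts marketed products as study drug, and SAP 15 counts the open-label tablet in compliance, so the H3 dose is study drug.

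**Safety tables.** SAP 18.1.1: "Incidence of TEAEs will be presented by System Organ Class (SOC) and Preferred Term (PT) and broken down further by maximum severity and relationship". SAP 18.1.6 adds CTC grade. Neither mentions study part. On columns, SAP 7 says tables "will first present the results in the active group (FEXPRESAR) and then the results in the placebo group". The safety set in SAP 5.5 comprises ITT subjects "who receive at least one dose of study medication and subjects will be classified according to treatment received", with no rule for a participant who receives placebo and later fexofenadine.

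**Window and collection.** The window wording in SAP 18.1 ("The treatment-emergent AE period starts at time of administration of study drug ends 3 days after administration of study drug") is the same in Protocol 9.3.5. Protocol 8.3.1 sets collection: "All AEs and SAEs will be collected from the signing of the informed consent form (ICF) until EOS". Section 4.1.7 puts EOS on Day 5.

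**The concern.** Every Arm B participant who completes dosing has had both placebo and fexofenadine, yet is shown in one column called placebo. An Arm B event that begins after the H3 dose and is judged related, or that is an AESI such as a systemic hypersensitivity reaction (SAP 18.1.5), would be tabulated under placebo although it followed the active drug. SAP 18.1.1.2 also counts a missing relationship as related. A reader of the table could not tell these events from ones that arose on placebo.

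Safety of fexofenadine started 2 days before exposure is a stated secondary objective (SAP 2.2). The only stretch in which one arm has had fexofenadine and the other only placebo runs from the first dose to H3, and no visible table isolates it. SAP 15 already reports compliance separately for the double-blind and open-label parts, so the distinction is built into the plan but not applied to adverse events.

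Separately, a window tied to the administration of study drug is ambiguous when there are three scheduled doses. Under some readings it extends past the point at which AEs are collected.

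**Working it through.** The plan gives no figure for exposure time by period, so there is nothing to reproduce. The check is arithmetic on the dosing and visit calendar.

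**Inputs from the documents.** Blinded doses on the mornings of Days 2 and 3; open-label dose at H3 on Day 4; EOS on Day 5; a 3-day window.

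**Assumed clock times (not in the documents).** Home dose 08:00, H0 09:00 (so H3 is 12:00), EOS contact 12:00. These were varied over: home dose 06:00-11:00, H0 08:00-13:00, EOS 08:00-17:00.

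**Step 1: Arm B time before and after fexofenadine.**
- Day 2 08:00 to Day 4 12:00 = 52 h on placebo only.
- Day 4 12:00 to Day 5 12:00 = 24 h after fexofenadine, up to EOS.
- Share of time to EOS = 24 / (52 + 24) = 24/76 = 32%.
- Lowest (dose 06:00, H0 13:00, EOS 08:00): 16 / (58 + 16) = 16/74 = 22%.
- Highest (dose 11:00, H0 08:00, EOS 17:00): 30 / (48 + 30) = 30/78 = 38%.

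**Step 2: the same share if the window closes 3 days after the first dose.**
- The window is 72 h and ends on Day 5 at 08:00, so 72 - 52 = 20 h follow the H3 dose.
- Share = 20/72 = 28%. Range: 14/72 = 19% to 24/72 = 33%.

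**Step 3: where the window ends, by anchor dose.**

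| Anchor dose | Window ends | Relative to EOS, assumed times | Range |
|---|---|---|---|
| First dose (Day 2) | Day 5 | 4 h before | 11 h before to 3 h after |
| Last blinded dose (Day 3) | Day 6 | 20 h after | 13 to 27 h after |
| H3 dose (Day 4) | Day 7 | 48 h after | 42 to 56 h after |

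The placebo column therefore contains post-fexofenadine time under every reading. The mismatch with AE collection depends on the reading: it essentially vanishes for the first dose and is about one or two days for the others.

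**The case against.** **The overall table answers the objective.** The stated aim concerns fexofenadine started 2 days before exposure, which is a question about regimens. Both arms take the same H3 dose, so the contrast after H3 is still randomised: two prior active doses against none. This stands. A reader might infer that the undivided table is biased or invalid; the documents do not support that. The column label and the missing view of the placebo-controlled period are the problem. The period before H3 also includes the 3 hours of pollen exposure, so events within it are not attributable to drug alone.

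**Time is not events.** The shares above are of time. They do not show how many events fall after H3, or that the arms would look more alike. Counting all 72 h after the H3 dose would give a larger share, but the hours past EOS have no systematic collection and cannot also add events to the placebo column.

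**The window may be harmless or already defined.** SAP 18.1.1.1 speaks of the first dose of study medication; if that is the anchor, the window ends at about EOS. The SAP contents list an algorithm for treatment emergence (Appendix 2) and a convention for presenting treatment groups (Appendix 1). Those pages and the table templates are not visible, so the anchor and the labels may be set there. This is a fair limit.

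**Low stakes.** Safety is descriptive with no between-arm tests (SAP 18), and listings carry Study Day (SAP 6.1), so events on other days can be separated by hand. Day 4 cannot be divided that way. This limits the importance of the point but does not remove it.

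**Conclusion.** The point holds as a cheap improvement to the safety tables. On the visible text, TEAEs are summarised under active and placebo columns over one period, and the placebo column contains Arm B time after fexofenadine: about 32% of time to EOS (22-38%), or about 28% (19-33%) if the window closes 3 days after the first dose. These figures rest on assumed clock times and on participants taking all scheduled doses. Related events or AESIs after H3 would sit under placebo, and no visible table shows the placebo-controlled period by itself.

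The window does not name its dose and ends on about Day 5, 6 or 7, against collection to EOS on Day 5. A reader might conclude that events on Days 5 to 7 would be lost. That follows only if the anchor is a later dose, and Appendix 2 may settle it. Nor do the documents show that the follow-up call in Protocol 8.3.3 would close the gap: it is described as following an initial report, so on its wording it covers events already reported. Efficacy, sample size and type I error are unaffected.

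**What to change.** In SAP 18.1:

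1. Keep the overall TEAE table, but label its columns active-active and placebo-active, the terms already used in the protocol synopsis.
2. Add TEAEs by onset period: first dose to just before the H3 dose, and from the H3 dose on. Include related events and AESIs in the split.
3. State a rule for Day 4 events with no onset time, for example a separate line. The H3 dose time is recorded (Protocol 6.3.1), but no visible text confirms that AE onset time is.
4. Name the dose that anchors the TEAE window and align its end with actual AE collection, for example by ending it at EOS, unless Appendix 2 already does so. Make the same change in Protocol 9.3.5 or record it in SAP 3.3.

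The cost is one extra table and a rule for missing onset times. Ending the window at EOS needs no new participant contact. Keeping a window beyond Day 5 would need a way to collect new events that the documents do not currently describe.
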